Stroke	2	V12.54, 433-436	I6300, I63011, I63012, I63013, I63019, I6302, I63031, I63032, I63033, I63039, I6309, I6310, I63111, I63112, I63113, I63119, I6312, I63131, I63132, I63133, I63139, I6319, I6320, I63211, I63212, I63213, I63219, I6322, I63231, I63232, I63233, I63239, I6329, I6330, I63311, I63312, I63313, I63319, I63321, I63322, I63323, I63329, I63331, I63332, I63333, I63339, I63341, I63342, I63343, I63349, I6339, I6340, I63411, I63412, I63413, I63419, I63421, I63422, I63423, I63429, I63431, I63432, I63433, I63439, I63441, I63442, I63443, I63449, I6349, I6350, I63511, I63512, I63513, I63519, I63521, I63522, I63523, I63529, I63531, I63532, I63533, I63539, I63541, I63542, I63543, I63549, I6359, I636, I638, I639, I6501, I6502, I6503, I6509, I651, I6521, I6522, I6523, I6529, I658, I659, I6601, I6602, I6603, I6609, I6611, I6612, I6613, I6619, I6621, I6622, I6623, I6629, I663, I668, I669

Table 6. CHADS₂-VASc Score

CHA ₂ DS ₂ –VASc	Point	ICD-9 Codes	ICD-10 Codes
Congestive Heart Failure	1	402.x1, 404.x1, 404.x3, 428.xx	I0981, I110, I132, I501, I5020, I5021, I5022, I5023, I5030, I5031, I5032, I5033, I5040, I5041, I5042, I5043, I509
Hypertension	1	401.xx-405.xx	I10, I110, I119, I120, I129, I130, I1310, I1311, I132, I150, I151, I152, I158, I159, I160, I161, I169, N262
Age ≥75 years	2	-	-
Diabetes mellitus	1	250, 357.2, 362.0, 366.41	E08311, E08319, E083211, E083212, E083213, E083219, E083291, E083292, E083293, E083299, E083311, E083312, E083313, E083319, E083391, E083392, E083393, E083399, E083411, E083412, E083413, E083419, E083491, E083492, E083493, E083499, E083511, E083512, E083513, E083519, E083521, E083522, E083523, E083529, E083531, E083532, E083533, E083539, E083541, E083542, E083543, E083549, E083551, E083552, E083553, E083559, E083591, E083592, E083593, E083599, E0836, E0840, E0842, E09311, E09319, E093211, E093212, E093213, E093219, E093291, E093292, E093293, E093299, E093311, E093312, E093313, E093319, E093391, E093392, E093393, E093399, E093411, E093412, E093413, E093419, E093491, E093492, E093493, E093499, E093511, E093512, E093513, E093519, E093521, E093522, E093523, E093529, E093531, E093532, E093533, E093539, E093541, E093542, E093543, E093549, E093551, E093552, E093553, E093559, E093591, E093592, E093593, E093599, E0936, E0940, E0942, E1010, E1011, E1021, E1022, E1029, E10311, E10319, E103211, E103212, E103213, E103219, E103291, E103292, E103293, E103299, E103311, E103312, E103313, E103319, E103391, E103392,

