Stroke (non-hemorrhagic only & transient ischemic attack)	2	V12.54, 433.xx-436.xx	I6300, I63011, I63012, I63013, I63019, I6302, I63031, I63032, I63033, I63039, I6309, I6310, I63111, I63112, I63113, I63119, I6312, I63131, I63132, I63133, I63139, I6319, I6320, I63211, I63212, I63213, I63219, I6322, I63231, I63232, I63233, I63239, I6329, I6330, I63311, I63312, I63313, I63319, I63321, I63322, I63323, I63329, I63331, I63332, I63333, I63339, I63341, I63342, I63343, I63349, I6339, I6340, I63411, I63412, I63413, I63419, I63421, I63422, I63423, I63429, I63431, I63432, I63433, I63439, I63441, I63442, I63443, I63449, I6349, I6350, I63511, I63512, I63513, I63519, I63521, I63522, I63523, I63529, I63531, I63532, I63533, I63539, I63541, I63542, I63543, I63549, I6359, I636, I638, I639, I6501, I6502, I6503, I6509, I651, I6521, I6522, I6523, I6529, I658, I659, I6601, I6602, I6603, I6609, I6611, I6612, I6613, I6619, I6621, I6622, I6623, I6629, I663, I668, I669
Vascular Disease (myocardial infarction, peripheral arterial disease, aortic	1	410.xx, 412, 440.xx, 441.xx, 442.xx, 443.xx, 444.2x, 445.0x	I200, I2101, I2102, I2109, I2111, I2119, I2121, I2129, I213, I214, I220, I221, I222, I228, I229, I240, I241, I248, I249, I25110, I252, I25700, I25710, I25720, I25730, I25750,

CHA2DS ₂ –VASc	Point	ICD-9 Codes	ICD-10 Codes

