Hypertension	1 point	401.xx-405.xx	I10, I110, I119, I120, I129, I130, I1310, I1311, I132, I150, I151, I152, I158, I159, I160, I161, I169, N262
Abnormal kidney and/or liver function:	1 point each	Kidney: 580.xx-589.xx	B520, E0821, E0822, E0829, E0921, E0922, E0929, M3214, M3215, M3504, N000, N001, N002, N003, N004, N005, N006, N007, N008, N009, N010, N011, N012, N013, N014, N015, N016, N017, N018, N019, N020, N021, N022, N023, N024, N025, N026, N027, N030, N031, N032, N033, N034, N035, N036, N037, N038, N039, N040, N041, N042, N043, N044, N045, N046, N047, N048, N049, N050, N051, N052, N053, N054, N055, N056, N057, N058, N059, N060, N061, N062, N063, N064, N065, N066, N067, N068, N069, N070, N071, N072, N073, N074, N075, N076, N077, N078, N079, N08, N140, N141, N142, N143, N144, N150, N158, N159, N16, N170, N171, N172, N178, N179, N181, N182, N183, N184, N185, N186, N189, N19, N250, N251, N2581, N2589, N259, N261, N269, N270, N271, N279
Age ≥75 years	2	Liver: 570.xx-573.xx	B251, K700, K7010, K7011, K702, K7030, K7031, K7040, K7041, K709, K710, K7110, K7111, K712, K713, K714, K7150, K7151, K716, K717, K718, K719, K7200, K7201, K7210, K7211, K7290, K7291, K730, K731, K732, K738, K739, K740, K741, K742, K743, K744, K745, K7460, K7469, K750, K751, K752, K753, K754, K7581, K7589, K759, K760, K761, K762, K763, K764, K765, K766, K767, K7681, K7689, K769, K77
Stroke	1 point	History of stroke V12.54, 433.xx-436.xx	G450, G451, G452, G458, G459, G460, G461, G462, I6300, I63011, I63012, I63013, I63019, I6302, I63031, I63032, I63033, I63039, I6309, I6310, I63111, I63112,

HAS-BLED	Point	ICD-9 Codes	ICD-10 Codes
			I63113, I63119, I6312, I63131, I63132, I63133, I63139, I6319, I6320, I63211, I63212, I63213, I63219, I6322, I63231, I63232, I63233, I63239, I6329, I6330, I63311, I63312, I63313, I63319, I63321, I63322, I63323, I63329, I63331, I63332, I63333, I63339, I63341, I63342, I63343, I63349, I6339, I6340, I63411, I63412, I63413, I63419, I63421, I63422, I63423, I63429, I63431, I63432, I63433, I63439, I63441, I63442, I63443, I63449, I6349, I6350, I63511, I63512, I63513, I63519, I63521, I63522, I63523, I63529, I63531, I63532, I63533, I63539, I63541, I63542, I63543, I63549, I6359, I636, I638, I639, I6501, I6502, I6503, I6509, I651, I6521, I6522, I6523, I6529, I658, I659, I6601, I6602, I6603, I6609, I6611, I6612, I6613, I6619, I6621, I6622, I6623, I6629, I663, I668, I669, I67841, I67848, Z8673

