	0D1A8ZH	Bypass Jejunum to Cecum, Via Natural or Artificial Opening Endoscopic
	0D1A8ZK	Bypass Jejunum to Ascending Colon, Via Natural or Artificial Opening Endoscopic
	0D1A8ZL	Bypass Jejunum to Transverse Colon, Via Natural or Artificial Opening Endoscopic
	0D1A8ZM	Bypass Jejunum to Descending Colon, Via Natural or Artificial Opening Endoscopic
	0D1A8ZN	Bypass Jejunum to Sigmoid Colon, Via Natural or Artificial Opening Endoscopic
	0D1A8ZP	Bypass Jejunum to Rectum, Via Natural or Artificial Opening Endoscopic
	0D1B0ZB	Bypass Ileum to Ileum, Open Approach
	0D1B0ZH	Bypass Ileum to Cecum, Open Approach
	0D1B0ZK	Bypass Ileum to Ascending Colon, Open Approach
	0D1B0ZL	Bypass Ileum to Transvers e Colon, Open Approach
	0D1B0ZM	Bypass Ileum to Descending Colon, Open Approach
	0D1B4ZN	Bypass Ileum to Sigmoid Colon, Percutaneous Endoscopic Approach
	0D1B4ZP	Bypass Ileum to Rectum, Percutaneous Endoscopic Approach
	0D1B4ZQ	Bypass Ileum to Anus, Percutaneous Endoscopic Approach
	0D1B8ZB	Bypass Ileum to Ileum, Via Natural or Artificial Opening Endoscopic
	0D1B8ZH	Bypass Ileum to Cecum, Vi a Natural or Artificial Opening Endoscopic

Type	Codes	Description
	0D1B8ZK	Bypass Ileum to Ascending Colon, Via Natural or Artificial Opening Endoscopic
	0D1B8ZL	Bypass Ileum to Transverse Colon, Via Natural or Artificial Opening Endoscopic
	0D1B8ZM	Bypass Ileum to Descending Colon, Via Natural or Artificial Opening Endoscopic
	0D1B8ZN	Bypass Ileum to Sigmoid Colon, Via Natural or Artificial Opening Endoscopic
	0D1B8ZP	Bypass Ileum to Rectum, Via Natural or Artificial Opening Endoscopic
	0D1B8ZQ	Bypass Ileum to Anus, Via Natural or Artificial Opening Endoscopic

Table 10. Charlson Comorbidity Index Score Calculation

Condition	ICD-9 Code(s)	ICD-10 Code(s)	Point
Myocardial Infarction	410.xx; 412.xx	I21, I22, I252	1
Congestive Heart Failure	428.xx	I43, I50, I099, I110, I130, I132, I255, I420, I425, I426, I427, I428, I429, P290	1
Peripheral vascular disease	441.xx; 443.9x; 785.4x; v43.4x, procedure : 38.48	I70, I71, I731, I738, I739, I771, I790, I792, K551, K558, K559, Z958, Z959	1
Cerebrovascular disease	430.xx-438.99 Modified to remove 430.xx-432.xx	G45, G46, I60, I61, I62, I63, I64, I65, I66, I67, I68, I69, H340	1
Dementia	290.xx	F00, F01, F02, F03, G30, F051, G311	1
Chronic obstructive pulmonary disease	490.xx-496.99; 500.xx-505.99; 506.4x	J40, J41, J42, J43, J44, J45, J46, J47, J60, J61, J62, J63, J64, J65, J66, J67, I278, I279, J684, J701, J703	1

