Transient ischemic attack (TIA)	435.x	G458, G459, Z8673
Coronary artery disease	410.xx-414.xx	I200, I201, I208, I209, I2101, I2102, I2109, I2111, I2119, I2121, I2129, I213, I214, I220, I221, I222, I228, I229, I240, I241, I248, I249, I2510, I25110, I25111, I25118, I25119, I252, I253, I2541, I2542, I255, I256, I25700, I25701, I25708, I25709, I25710, I25711, I25718, I25719, I25720, I25721, I25728, I25729, I25730, I25731, I25738, I25739, I25750, I25751, I25758, I25759, I25760, I25761, I25768, I25769, I25790, I25791, I25798, I25799, I25810, I25811, I25812, I2582, I2583, I2584, I2589, I259
Anemia and coagulation defects	280.xx-286.xx	D50-D53, D55-D59, D60-D69,

Table 12. Clinical Outcomes

Outcome Variables		ICD-9-CM/Procedure Codes	ICD-10-CM Codes/Procedure Codes
Stoke/ SE	Hemorrhagic Stroke	430.xx-432.xx Cases will be excluded if traumatic brain injury (ICD-9: 800-804, 850-854) was present during hospitalization.	I6000, I6001, I6002, I6010, I6011, I6012, I602, I6030, I6031, I6032, I604, I6050, I6051, I6052, I606, I607, I608, I609, I610, I611, I612, I613, I614, I615, I616, I618, I619; Cases will be excluded according to Table 12.
	Ischemic Stroke	433.x1, 434.x1, 436	I6300, I63011, I63012, I63013, I63019, I6302, I63031, I63032, I63033, I63039, I6309, I6310, I63111, I63112, I63113, I63119, I6312, I63131, I63132, I63133, I63139, I6319, I6320, I63211, I63212, I63213, I63219, I6322, I63231, I63232, I63233, I63239, I6329, I6330, I63311, I63312, I63313, I63319, I63321, I63322, I63323, I63329, I63331, I63332, I63333, I63339, I63341, I63342, I63343, I63349, I6339, I6340, I63411, I63412, I63413, I63419, I63421, I63422, I63423, I63429, I63431, I63432, I63433, I63439, I63441, I63442, I63443, I63449, I6349, I6350, I63511, I63512, I63513, I63519, I63521, I63522, I63523, I63529, I63531, I63532, I63533, I63539, I63541, I63542, I63543, I63549, I6359, I636, I638, I639, I6789
	Systemic	444.x, 445.x	I7401, I7409, I7410, I7411, I7419, I742, I743,

Outcome Variables		ICD-9-CM/Procedure Codes	ICD-10-CM Codes/Procedure Codes
	Embolism		I744, I745, I748, I749, I75011, I75012, I75013, I75019, I75021, I75022, I75023, I75029, I7581, I7589

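### The stroke item of CHADS2, CHA2DS2-VASc and HAS-BLED accepts stenosis codes that the plan's own stroke and TIA definitions leave out, and in two of the scores it loses TIA and history codes under ICD-10

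*Combined protocol and SAP*

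**What the plan says.** The three risk scores are baseline variables (Section 9.3, Table 1), computed from the point and code lists in the Appendix. Baseline is the 6 months up to and including the index date. Codes count in any position unless a variable says otherwise.

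The stroke items read as follows.

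- **Table 5, CHADS2, 2 points.** Labelled simply as stroke. ICD-9: "V12.54, 433-436".
- **Table 6, CHA2DS2-VASc, 2 points.** Labelled "Stroke (non-hemorrhagic only & transient ischemic attack". ICD-9: "V12.54, 433.xx-436.xx".
- **Table 7, HAS-BLED, 1 point.** Labelled simply as stroke. ICD-9: "History of stroke V12.54, 433.xx-436.xx".

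In all three ICD-10 cells the I63 codes run straight on into I65 and I66, as in "I638, I639, I6501, I6502, I6503, I6509, I651, I6521, I6522, I6523, I6529, I658, I659".

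Elsewhere the plan is narrower. Table 12 defines the ischemic stroke outcome in ICD-9 as "433.x1, 434.x1, 436", and in ICD-10 as the I63 codes plus I6789. Table 11 defines TIA as 435.x in ICD-9 and as G458, G459 and Z8673 in ICD-10. The baseline covariate for history of stroke/SE in Table 11 points to the Table 12 list.

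**The concern.** An item that scores prior stroke (and, in Table 6, TIA) should be met by codes for stroke or TIA. In standard ICD nomenclature, 433/434 codes with fifth digit 0 and the I65 and I66 families denote occlusion or stenosis without infarction. The documents do not spell out these meanings. They do show that the plan separates the two groups when it defines its outcome, since Table 12 restricts 433 and 434 to fifth digit 1 and omits I65 and I66.

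Because any diagnosis position counts, one secondary code for carotid stenosis is enough to score the item. It carries 2 of the points in CHADS2 and CHA2DS2-VASc.

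The same item also behaves differently by coding system in Tables 5 and 6. ICD-9 data can score through TIA (435) or history (V12.54). ICD-10 data cannot score through any of the codes that Table 11 uses for TIA.

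What is at stake is the description of stroke and bleeding risk under Aim 1, a primary objective, and the comparability of the scores between patients coded in ICD-9 and in ICD-10.

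**Working it through.** The plan states no figure on this point, so there is nothing to reproduce. The check compares code lists, then shows what the mismatch does to a mean score under stated assumptions.

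**Step 1. Compare the ICD-10 lists.** The stroke cells of Tables 5, 6 and 7 were compared as sets with the ischemic stroke list in Table 12 and the TIA list in Table 11.

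| ICD-10 stroke item | Table 5 | Table 6 | Table 7 |
|---|---|---|---|
| Codes listed | 116 | 116 | 127 |
| of which I63 | 90 | 90 | 90 |
| of which I65/I66 | 26 | 26 | 26 |
| I65/I66 codes also in Table 12 ischemic stroke | 0 | 0 | 0 |
| I65/I66 codes also in Table 11 TIA | 0 | 0 | 0 |
| G458, G459, Z8673 present | 0 of 3 | 0 of 3 | 3 of 3 |

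Tables 5 and 6 are identical. Table 7 has 11 further codes (127 − 116): G450, G451, G452, G458, G459, G460, G461, G462, I67841, I67848 and Z8673.

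**Step 2. Compare the ICD-9 lists.** All three items take 433 to 436 without a fifth-digit limit. Table 12 keeps 433.x1, 434.x1 and 436, and Table 11 assigns 435.x to TIA. What remains in the score items, covered by neither definition, is every 433 and 434 code with a fifth digit other than 1. V12.54 is in all three items.

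**Step 3. Effect on one patient.** If the only qualifying code is one of those, the patient gains 2 points on CHADS2, 2 on CHA2DS2-VASc and 1 on HAS-BLED. A patient who also has an I63 code, or 433.x1 or 434.x1, scores the same with or without the stenosis codes.

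**Step 4. Effect on a mean.** Let p be the share of patients who qualify only through a stenosis code. The mean rises by points × p. The documents give no p, so these values are assumptions:

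| Assumed p | CHADS2 and CHA2DS2-VASc (2p) | HAS-BLED (1p) |
|---|---|---|
| 1% | 0.02 | 0.01 |
| 5% | 0.10 | 0.05 |
| 10% | 0.20 | 0.10 |

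**Step 5. The TIA/history gap.** Among patients coded in ICD-10, let q be the share whose only evidence is G458, G459 or Z8673. In CHADS2 and CHA2DS2-VASc they lose 2 points each, so the net shift in the mean is 2(p − q). With p and q each assumed to lie between 1% and 10%, it runs from 2(0.01 − 0.10) = −0.18 to 2(0.10 − 0.01) = +0.18. If p equals q the mean is unchanged, but a share p + q of those patients is still misclassified. HAS-BLED does not have this gap, because Table 7 lists all three codes.

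**The case against.** The strongest reply is that this is one yes/no item in each score, that it affects only patients with no other qualifying code, and that the main adjustment does not depend on it. Most of that stands, and it rules out several stronger readings.

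- **That all three scores are simply wrong.** Only the stroke item is affected, and only for some patients. The other items are not touched by this point.
- **That the apixaban–warfarin comparison is biased.** The documents do not support this. Section 9.7.1 leaves the propensity covariates to clinical rationale and never says that these scores enter the model. History of stroke/SE, on Table 12 codes, and TIA are separate baseline covariates. The scores could still enter, because the list is open and unbalanced variables go into the Cox models, but that is a possibility and not a stated plan.
- **That late-effect codes (438, I69) must be added.** No section requires it. The Charlson cerebrovascular item does reach them ("430.xx-438.99 Modified to remove 430.xx-432.xx" in ICD-9, and I69 in ICD-10), but it is a broader construct that also takes I65 and I66. Because 438 does not separate stroke types, adding it would sit badly with Table 6's restriction to non-hemorrhagic stroke.
- **That the baseline table will contradict itself.** History of stroke/SE covers hemorrhagic stroke and systemic embolism and leaves out TIA, so it would differ from the score items even after correction.

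The objection does not justify the stenosis codes. They fit neither the item labels nor the plan's own stroke and TIA lists. Nor does it explain why TIA and history count in one coding system and not in the other.

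**Conclusion.** The point holds in limited form. The stroke items in Tables 5 to 7 admit 26 I65/I66 codes, and all non-infarction 433/434 codes, that the plan excludes from both ischemic stroke and TIA. Patients who qualify only on such a code are recorded as prior stroke. In Tables 5 and 6 the ICD-10 cell also lacks the three TIA/history codes, although the ICD-9 cell counts TIA and history, Table 6's label names TIA, and Table 7 lists all three.

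The direction of each error is clear: stenosis codes push the scores up, and the ICD-10 gap pushes CHADS2 and CHA2DS2-VASc down. The size of either is unknown, because it depends on shares that the documents do not give; the 1% to 10% range is an assumption. The consequence that can be shown is misclassification in the risk scores reported under Aim 1. Nothing here shows an effect on the hazard ratios.

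The comparison of lists rests on the documents alone. Describing the extra codes as stenosis without infarction rests on standard ICD nomenclature.

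**What to change.** In the stroke rows of the Appendix:

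1. Tables 5, 6 and 7, ICD-9: replace the 433 to 436 range with 433.x1, 434.x1, 435.x and 436, and keep V12.54.
2. Tables 5, 6 and 7, ICD-10: delete every I65 and I66 code.
3. Tables 5 and 6, ICD-10: add G458, G459 and Z8673, so that TIA and history count in both coding systems.
4. If stenosis is wanted for adjustment, carry it as its own baseline flag.

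The ICD-10 cells then hold 116 − 26 + 3 = 93 codes in Tables 5 and 6, and 127 − 26 = 101 in Table 7. The 8 codes by which Table 7 still differs are G450 to G452, G460 to G462, I67841 and I67848; a sentence saying whether that difference is intended would close the matter.

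The cost is an edit to the code cells and a rerun of the three scores. No new data are needed.

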2. LIST OF ABBREVIATIONS

Abbreviation	Definition
AE	adverse event
AF	atrial fibrillation
ARIC	Atherosclerosis Risk in Communities
BMI	body mass index
CCI	[REDACTED]
CHADS ₂	Acronym: congestive heart failure, hypertension, age 75 years or older, diabetes mellitus
CMS	Center of Medicare Services
CPI	Consumer Price Index
CPT	Current Procedural Terminology
CrCl	creatinine clearance rate
DME	durable medical equipment
DOAC	direct oral anticoagulant
DSS	Decision Support System
EDB	enrollment database
ER	emergency room
GHP	group health plan
GLM	generalized linear models
GPP	Good Pharmacoepidemiology Practices
HAS-BLED	Hypertension, Abnormal Renal/Liver Function, Stroke, Bleeding, Labile INR, Elderly (Age >65 years), Drugs or Alcohol
HCFA	Health Care Financing Agency
HCPCS	Healthcare Common Procedure Coding System
HCRU	Healthcare resource utilization
HHA	Home Health Agency
HR	hazard ratios
ICD-9-CM	International Classification of Disease, Ninth Revision, Clinical Modification
ICD-10-CM	International Classification of Disease, Tenth Revision, Clinical Modification
ICH	intracranial hemorrhage
IPTW	inverse probability treatment weightings
INR	international normalized ratio
LAB	laboratory
LAR	labatory results
LOS	length of stay
MB	major bleeding
NDE	non-destructive examinations
NVAF	non-valvular atrial fibrillation
OAC	oral anticoagulant

Abbreviation	Definition
PHA	pharmacy
PPPM	per patient per month
RAD	radiology
RIF	research identifiable file
RWD	real world data
SE	systemic embolism
SNF	skilled nursing facility
SSN	social security number
TTR	time in therapeutic range
USD	United States dollar
VA	Veterans' Affairs
VHA	Veterans' Health Affairs
VKA	Vitamin K antagonist

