9.3. Variables

Baseline variables during the 6 months prior to, and on, the index date will be measured. Baseline variables will be evaluated using codes in any position unless noted otherwise.

Table 1. Baseline Demographic and Clinical Characteristic Variables

Variable	Data Source(s)	Operational Definition
Age	Both VA and Medicare	Age will be defined as of the index date and used to assign patients to age groups (eg, 18-54, 55-64, 65-74, 75-79, \geq 80 years).
Sex	Both VA and Medicare	A flag will be created for female beneficiaries and reported as a percentage.
US Geographic Region	Both VA and Medicare	The United States will be divided into 5 regions: Northeast, South, Midwest, West, and Other.
Race	Both VA and Medicare	Race will be identified and will be categorized as: White, Black, Other, and unknown.
Year of index OAC	Both VA and Medicare	A flag will be created for proportion of unique patients with index OAC identified in 2013, 2014, 2015, 2016, and 2017.

Variable	Data Source(s)	Operational Definition
Dose of Index DOAC	Both VA and Medicare	-Standard dose (apixaban 5 mg, dabigatran 150 mg, and rivaroxaban 20 mg) based on dose of the initial prescription of DOAC; -lower dose (apixaban 2.5 mg, dabigatran 75 mg, rivaroxaban 15 mg/10 mg) based on dose of the initial prescription of DOAC.
Body Weight	VA	Body weight will be obtained as continuous and categorical variables. The categories will be: ≤ 60 kg, 61-99 kg, 100-119 kg, and ≥ 120 kg. If a patient has multiple values, the value closest to the index date will be used.
BMI	VA	Body Mass Index: Body mass index will be calculated as weight in kilograms divided by the square of height in meters. Mean, median, and standard deviation will be provided for the continuous variable. The categories will be <18.5 , 18.5-24.9, 25-29.9, 30-39, and ≥ 40 . If a patient has multiple values, the value closest to the index date will be used.
Creatinine Clearance	VA	Creatinine Clearance: Creatinine clearance will be identified using LOINC codes (2160-0, 33914-3, 48642-3, 48643-1, 62238-1, 2164-2, 14682-9). A categorical variable for the glomerular filtration rate (GFR) will be created with the following cutoff points: <15 ml/min, 15-29 ml/min, 30-59 ml/min, 60-89 ml/min, and ≥ 90 ml/min. If a patient has multiple values, the value closest to the index date will be used. The creatinine clearance rate (CrCl) will be calculated based on serum creatinine for patients who only had serum creatinine information. ²⁵

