INR	VA	International Normalized Ratio Test Results will be identified using Logical Observation Identifiers Names and Codes (LOINC; 34714-6, 38875-1, 46418-0, 52129-4, 5895-7, 5896-5, 61189-7, 6301-6, 72281-9) occurring anytime during the baseline period will be evaluated.
CHADS₂ Score	Both VA and Medicare	CHADS ₂ Score will be calculated according to the points algorithm outlined in Appendix Table 5 .

Variable	Data Source(s)	Operational Definition
CHA2DS₂-VASc Score	Both VA and Medicare	CHA2DS ₂ -VASc score will be calculated according to the points algorithm outlined in Appendix Table 6 .
HAS-BLED Score	Both VA and Medicare	HAS-BLED score will be calculated according to the points algorithm outlined in Appendix Table 7 .
Baseline Medication Use	Both VA and Medicare	A flag will be created for the following medications prescribed during the baseline period: angiotensin-converting enzyme inhibitors/ angiotensin-receptor blockers, aspirin, beta blockers, statins, proton pump inhibitors, H ₂ -receptor antagonists, antiplatelets, nonsteroidal anti-inflammatory drugs, inhibitors of warfarin, inducers of warfarin, dronedarone, digoxin, calcium channel blockers, renin angiotensin system antagonists, glucocorticoids, diuretics, metformin, sulfonylureas, thiazolidinedione, insulin, other diabetes drugs, antiulcer agents, and antidepressants (See Appendix Table 8 for codes).
Bariatric Surgery	Both VA and Medicare	A flag will be created for patients with claims for bariatric surgery (See Appendix Table 9 for codes).
CCI	Both VA and Medicare	Charlson Comorbidity index will be calculated as a continuous variable (See Appendix Table 10 for calculation and codes).
Comorbid Conditions	Both VA and Medicare	The following comorbid conditions will be flagged in baseline: History of stroke/SE, history of bleeding, myocardial infarction, renal disease, liver disease, dyspepsia or stomach discomfort, diabetes, hypertension, congestive heart failure, non-stroke/SE peripheral vascular disease, anemia and coagulation defects , transient ischemic attack, coronary artery disease, peripheral artery disease (See Appendix Table 11 for codes).

Table 2. Clinical and Outcome Variables

Variable	Data Source(s)	Operational Definition

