9.7.1. Analysis Plan for Primary Objective

Baseline demographic and clinical factors such as age, sex, geographic region, baseline medications, and co-morbidities among NVAf patients initiating OAC will be summarized. Descriptive statistics, (ie, mean, standard deviation, median, and inter-quartile range for continuous variables and differences across treatments) will be compared using the Student's t-test or Wilcoxon rank sum test. Percentages for categorical and binary variables will be presented for all baseline patient characteristics and will be compared using the chi-square test or Fisher's Exact test.

The cumulative incidence rate for clinical outcomes (stroke/SE, MB, net clinical benefit) will be calculated. MB will be stratified by GI bleeding, ICH, and other bleeding; Stroke/SE will be stratified by hemorrhagic, ischemic, and systemic embolism. The incidence rate will be calculated as the number of patients who experience the event divided by the observed time at risk. The incidence rate will be calculated per 100 person-years.

Inverse Probability Treatment Weighting (IPTW)

Inverse probability treatment weighting (IPTW) will be used to balance patient characteristics when comparing outcomes among different cohorts. Three sets of IPTW will be conducted (all patients, obese patients, and severely obese patients). Depending on sample size, IPTW will also be conducted for the standard dose patients separately. In addition, the primary analysis will be conducted for apixaban vs warfarin and depending on the sample size, other OAC comparisons will be conducted.

IPTW uses propensity scores to obtain estimates of the average treatment effect. The propensity score will be calculated using a logistic model with treatment cohorts included in the model, using warfarin patients as the reference (ie, control cohort). The propensity score is defined as the probability of a patient receiving a certain treatment or not conditional on their observed baseline covariates (eg, age, gender, comorbidities, medications, etc.). The list of variables included in the logistic model will be based on clinical rationale. The propensity score acts as a balancing score between the cohorts. After calculating the propensity score, the distribution of the propensity scores will be reviewed. Each patient will be weighted by the inverse of the probability of their treatment option (weight=1/propensity score).

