plaque)			I25760, I25790, I670, I700, I701, I70201, I70202, I70203, I70208, I70209, I70211, I70212, I70213, I70218, I70219, I70221, I70222, I70223, I70228, I70229, I70231, I70232, I70233, I70234, I70235, I70238, I70239, I70241, I70242, I70243, I70244, I70245, I70248, I70249, I7025, I70261, I70262, I70263, I70268, I70269, I70291, I70292, I70293, I70298, I70299, I70301, I70302, I70303, I70308, I70309, I70311, I70312, I70313, I70318, I70319, I70321, I70322, I70323, I70328, I70329, I70331, I70332, I70333, I70334, I70335, I70338, I70339, I70341, I70342, I70343, I70344, I70345, I70348, I70349, I7035, I70361, I70362, I70363, I70368, I70369, I70391, I70392, I70393, I70398, I70399, I70401, I70402, I70403, I70408, I70409, I70411, I70412, I70413, I70418, I70419, I70421, I70422, I70423, I70428, I70429, I70431, I70432, I70433, I70434, I70435, I70438, I70439, I70441, I70442, I70443, I70444, I70445, I70448, I70449, I7045, I70461, I70462, I70463, I70468, I70469, I70491, I70492, I70493, I70498, I70499, I70501, I70502, I70503, I70508, I70509, I70511, I70512, I70513, I70518, I70519, I70521, I70522, I70523, I70528, I70529, I70531, I70532, I70533, I70534, I70535, I70538, I70539, I70541, I70542, I70543, I70544, I70545, I70548, I70549, I7055, I70561, I70562, I70563, I70568, I70569, I70591, I70592, I70593, I70598, I70599, I70601, I70602, I70603, I70608, I70609, I70611, I70612, I70613, I70618, I70619, I70621, I70622, I70623, I70628, I70629, I70631, I70632, I70633, I70634, I70635, I70638, I70639, I70641, I70642, I70643, I70644, I70645, I70648, I70649, I7065, I70661, I70662, I70663, I70668, I70669, I70691, I70692, I70693, I70698, I70699,

CHA2DS ₂ -VASc	Point	ICD-9 Codes	ICD-10 Codes
			I70701, I70702, I70703, I70708, I70709, I70711, I70712, I70713, I70718, I70719, I70721, I70722, I70723, I70728, I70729, I70731, I70732, I70733, I70734, I70735, I70738, I70739, I70741, I70742, I70743, I70744, I70745, I70748, I70749, I7075, I70761, I70762, I70763, I70768, I70769, I70791, I70792, I70793, I70798, I70799, I708, I7090, I7091, I7092, I7100, I7101, I7102, I7103, I711, I712, I713, I714, I715, I716, I718, I719, I720, I721, I722, I723, I724, I725, I726, I728, I729, I7300, I7301, I731, I7381, I7389, I739, I742, I743, I744, I75011, I75012, I75013, I75019, I75021, I75022, I75023, I75029, I7770, I7771, I7772, I7773, I7774, I7775, I7776, I7777, I7779, I790, I791, I798
Age	1	Age 65-75 years	-
Sex Category	1 (Female)	-	-

Table 7. HAS-BLED Score

HAS-BLED	Point	ICD-9 Codes	ICD-10 Codes

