			M25069, M25071, M25072, M25073, M25074, M25075, M25076, M2508, M96810, M96811, M96830, M96831, N421, N837, N857, N920, N9961, N9962, N99820, N99821, R040, R041, R042, R0489, R049, R310, R319, R58, R710, S0190XA, S062X0A, S062X1A, S062X2A, S062X3A, S062X4A, S062X5A, S062X6A, S062X7A, S062X8A, S062X9A, S06300A, S06301A, S06302A, S06303A, S06304A, S06305A, S06306A, S06307A, S06308A, S06309A, S06340A, S06341A, S06342A, S06343A, S06344A, S06345A, S06346A, S06347A, S06348A, S06349A, S06350A, S06351A, S06352A, S06353A, S06354A, S06355A, S06356A, S06357A, S06358A, S06359A, S06360A, S06361A, S06362A, S06363A, S06364A, S06365A, S06366A, S06367A, S06368A, S06369A, S064X0A, S064X1A, S064X2A, S064X3A, S064X4A, S064X5A, S064X6A, S064X7A, S064X8A, S064X9A, S065X0A, S065X1A, S065X2A, S065X3A, S065X4A, S065X5A, S065X6A, S065X7A, S065X8A, S065X9A, S066X0A, S066X1A, S066X2A, S066X3A, S066X4A, S066X5A, S066X6A, S066X7A, S066X8A, S066X9A, S06890A, S06891A, S06892A, S06893A, S06894A, S06895A, S06896A, S06897A, S06898A, S06899A, S069X0A, S069X1A, S069X2A, S069X3A, S069X4A, S069X5A, S069X6A, S069X7A, S069X8A, S069X9A, S36112A, S37021A, S37022A, S37029A, T792XXA
Labile INR	Not applicable	Not measurable.	Not applicable
Elderly	1 point for age 65 or older	65+ years	65+ years
Alcohol/ Drug Therapy	1 point	303.xx, 305.0x, V11.3x Antiplatelets administered (abciximab, anagrelide HCL, aspirin, aspirin/dipyridamole,	F1010, F10120, F10129, F1020, F1021, F10220, F10229

HAS-BLED	Point	ICD-9 Codes	ICD-10 Codes
		cilostazol, clopidogrel, dipyridamole, eptifibatide, prasugrel, ticagrelor, ticlopidine, tirofiban) NSAIDs administered (bromfenac, celecoxib, diclofenac, etodolac, fenoprofen, flurbiprofen, ibuprofen, indomethacin, ketoprofen, ketorolac, lansoprazole/naproxen, meclofenamate, mefenamic acid, meloxicam, nabumetone, naproxen, oxaprozin, piroxicam, sulindac, tolmetin)	

Table 8. Baseline Medication List

Mechanism of Action	Drug	
Angiotensin converting enzyme inhibitor	Benazepril, Captopril, Enalapril, Fosinopril, Lisinopril, Moexipril, Perindopril, Quinapril, Ramipril, Trandolapril	
Amiodarone	Amiodarone	
Angiotensin receptor blocker	Azilsartan, Candesartan, Eprosartan, Irbesartan, Losartan, Olmesartan, Telmisartan, Valsartan	
Beta blockers	Acebutolol, Atenolol, Betaxolol, Bisoprolol, Esmolol, Carteolol, Carvedeolol, Labetalol, Levobunolol, Metipranolol, Metoprolol, Nebivolol, Nadolol, Penbutolol, Pinodolol, Propranolol, Sotalol, Timolol,	

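### The CHA2DS2-VASc age rows in Appendix Table 6 overlap at 75, so a patient aged exactly 75 scores 3 age points when the rows are summed as written

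*Combined protocol and SAP*

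**What the plan says.** Table 1 (section 9.3) defines CHADS2, CHA2DS2-VASc and HAS-BLED in the same way, each by reference to its own appendix table: "Score will be calculated according to the points algorithm outlined in Appendix" Tables 5, 6 and 7 respectively. The appendix tables are therefore the operational scoring rules.

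Table 6 (section 17.1) has two separate age rows for CHA2DS2-VASc. The first assigns 2 points from age 75 upwards. The second, further down, assigns 1 point and is defined as "Age 65-75 years". No note says that only one of the two may count.

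Elsewhere the plan puts the boundary between 74 and 75: the age groups in Table 1 are given as "18-54, 55-64, 65-74, 75-79" and 80 or over.

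In Table 7 (HAS-BLED), the codes "Liver: 570.xx-573.xx" appear beside a label for age 75 or over and the value 2. The row above gives one point apiece for abnormal kidney and liver function, and a separate Elderly row gives "1 point for age 65 or older".

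**The concern.** A scoring table should place every patient in one age category, and the age contribution should not fall as age rises. Table 6 fails on both counts at a single age. A programmer who codes each row as an independent flag and adds the points will give a 75-year-old more age points than a 90-year-old. A programmer who uses if/else logic will not. The plan does not choose between them, so two programmers working from the same table could produce different scores for the same patients.

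What is at stake is the accuracy of one baseline descriptor. CHA2DS2-VASc is among the clinical characteristics that Aim 1 reports for the obese and severely obese cohorts.

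**Working it through.** The plan states no figure that depends on this rule, so there is nothing to reproduce. The check is to apply the rows as written.

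**Inputs from Table 6.** Age 75 or over: 2 points. Lower age row, 65 to 75 inclusive: 1 point. Other items: heart failure 1, hypertension 1, diabetes 1, stroke 2, vascular disease 1, female sex 1.

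**Assumptions not in the documents.** Age is held in completed years at the index date. The share of patients aged exactly 75, p, lies between 2% and 6%.

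**Age points by age:**

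| Age | Upper row | Lower row | Sum as written | With lower row 65-74 |
|---|---|---|---|---|
| 64 | 0 | 0 | 0 | 0 |
| 65 | 0 | 1 | 1 | 1 |
| 74 | 0 | 1 | 1 | 1 |
| 75 | 2 | 1 | 3 | 2 |
| 76 | 2 | 0 | 2 | 2 |
| 80 | 2 | 0 | 2 | 2 |

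Only age 75 changes, by 3 − 2 = 1 point.

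**Table maximum.** Non-age items: 1 + 1 + 1 + 2 + 1 + 1 = 7. With exclusive age rows the maximum is 7 + 2 = 9. As written it is 7 + 3 = 10, reachable only at age 75.

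**Shift in the mean.** Shift = p × 1 point. For p = 0.02, 0.04 and 0.06 the shift is 0.02, 0.04 and 0.06.

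**Effect on the balance check.** Section 9.7.1 treats a standardized difference below 10% as balanced. Take a standard deviation of 1.5 points (an assumption) and the extreme case in which the mis-scored patients all fall in one cohort. The overlap then adds at most 0.06 / 1.5 = 0.04 to the standardized difference, under half the threshold.

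**The other two scores.** Table 5 (CHADS2) has a single age row, so no overlap is possible. Table 7 has one clear age item, the Elderly row.

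**The case against.** The strongest reply is that no competent programmer would add both rows. Table 1 already puts age 75 in the upper group, and section 9.8 provides for clinical review of the coding strategy and double programming of parts of the dataset. That is fair, and it lowers the chance that the error reaches the output. It does not correct the table, which is the stated algorithm. Double programming would at best expose a disagreement that the plan gives no rule to settle.

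The reply also holds on consequence. Section 9.7.1 says only that "The list of variables included in the logistic model will be based on clinical rationale"; its examples are age, gender, comorbidities and medications. The matching analysis in section 9.7.2 names age, region, the Charlson index, comorbidities and other clinical characteristics. Neither section names CHA2DS2-VASc or HAS-BLED, and age is itself listed in both. A reader might infer that the overlap biases the weighting or a hazard ratio. The documents do not support that: they neither include nor exclude the score, and nothing suggests the share aged 75 differs between apixaban and warfarin patients.

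A reader might also infer from the Table 7 label that HAS-BLED is wrong for everyone aged 75 or over. Scored as an extra age item, the label would add 2 points to each such patient; with an assumed 30% to 60% aged 75 or over, the mean would rise by 2 × 0.30 = 0.6 to 2 × 0.60 = 1.2. The documents do not support resting anything on that figure. The label sits where the label and point cells of a combined kidney/liver item would be merged or blank, and it matches the Table 6 age row. It may therefore be a displaced cell from reading the PDF rather than an error in the plan. Even if it is real, the row holds liver codes, the row above already sets the liver score at one point, and Elderly has its own row.

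**Conclusion.** The point holds for Table 6 alone. As written, CHA2DS2-VASc gives 3 age points at exactly 75 and 2 at every older age. The size is 1 point for patients of that one age, or about 0.02 to 0.06 on the mean if 2% to 6% of patients are aged 75. It arises only if the rows are summed literally and age is in whole years. The consequence shown is confined to a baseline descriptor; no effect on the propensity model, any hazard ratio or the study size is shown. It is a minor specification slip, worth correcting because the correction is unambiguous from the plan's own age groups. CHADS2 is unaffected. HAS-BLED is an open query, not a finding.

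**What to change.** In Table 6, change the lower age row to 65-74 years, so that the two rows are exclusive and agree with Table 1. This costs one cell edit, has no analytic downside, and leaves the score at every age other than 75 unchanged.

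As a query, check the source of Table 7. If the liver-code row really carries a label for age 75 or over and the value 2, reconcile it with the one point each for kidney and liver and with the separate Elderly row. If it does not, nothing needs to change there.

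While the appendix is open, the abbreviation list could be aligned too: it expands HAS-BLED with "Elderly (Age >65 years", whereas Table 7 counts from 65. The table is the operative definition, so this is tidying only.
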